4.3.1 Patient Retention

Study participants will not be directly financially compensated and will incur the standard fees for evaluation and treatment. To decrease the financial burden and increase follow-up, however, the following as described will be provided for study participants:

- Systemic antibiotics (Ceftriaxone) cost during first hospital stay will be covered for all patients screened for the study
- Gentamicin (intervention arm only), saline solution, and injection materials (syringes, needles) will be covered for all participants
- Preoperative, postoperative, and 2-week creatinine levels will be covered for all participants
- C-reactive protein (CRP) levels will be covered for all participants
- Radiograph cost: Radiographs of the affected extremity will be obtained at the time of presentation and at post-operative follow-up appointments to adequately monitor healing. Imaging costs will be covered for all study participants.
- Post-operative consultation fees: consultation fees for study participant follow-up clinical evaluations will be waived for study participants.
- Follow-up visits will take place in a dedicated study clinic to minimize wait times
- Three separate contacts will be obtained for each patient upon enrollment.
- Follow-up clinic visit reminders will be given via phone call and by text message during the week prior to each visit
- Reoperation fees: The cost of two intraoperative cultures will be covered for study participants who undergo reoperation.

4.4 Schedule of Events:

Following participant enrollment and informed consent, baseline clinical and demographic data are collected from the patient including socioeconomic status, medical and social history, injury characteristics, and estimated pre-injury health-related quality of life. Contact information for the patient and at least two close contacts is collected to optimize follow-up. Pre- and post-operative

radiographs will be obtained prior to hospital discharge and serum creatinine will be obtained pre-operatively and on postoperative day 2. If serum creatinine levels on postoperative day 2 are ≥ 1.5 times patient baseline and acute kidney injury is suspected, serum creatinine levels will be redrawn at two-week follow-up visit¹⁸. Personnel time and resources utilized will be directly observed using time and motion analysis, beginning from patient admission to the completion of surgery and transfer to the ward. The schedule of patient encounters and corresponding data to be collected is described in Table 2.

Participants will return to clinic for follow-up at 2 weeks, 6 weeks, 3 months, 6 months, 9 months, and 1 year following surgery.

Specifically, follow-up visits will include the following:

1. Two-week postoperative visit: The study investigator will review and record interval history since hospital discharge. The patient will complete a Visual Analog Scale for pain assessment. A physical examination will be performed to assess for signs of Fracture-related Infection. C-reactive protein level will be obtained. If serum creatinine levels on postoperative day 2 are ≥ 1.5 times patient baseline and acute kidney injury is suspected, serum creatinine levels will be redrawn.
2. Six-week postoperative visit: During the follow-up visit reminder telephone phone call, the study investigator will ask the five fracture-related infection (FRI) validation questions. At the visit, the study investigator will review and record interval history since the last appointment. The patient will complete a Visual Analog Scale for pain assessment. The study subject will complete a Work Productivity and Activity Impairment questionnaire (WPAI) to assess lost productivity, and patient reported outcome measure (EQ-5D). A physical examination will be performed to assess for signs of fracture-related infection (FRI). C-reactive protein level will be obtained.
3. Three-month, six-month, nine-month, and 12-month postoperative visits: During the follow-up visit reminder telephone phone call, the study investigator will ask the five fracture-related infection (FRI) validation questions. At the visit, the study investigator will review and record interval history since the last appointment. The patient will complete a Visual Analog Scale for pain assessment. The study subject will complete a Work and Activity Impairment questionnaire (WPAI), the FIX-IT score for clinical healing, additional questions to address indirect costs and economic impact associated with their treatment, and patient reported outcome measure (EQ-5D). A physical examination will be performed to assess for signs of fracture-related infection (FRI). AP and lateral radiographs will be taken. C-reactive protein level will be obtained.

Table 2: Schedule of Events

Assessment	Hospital			Outpatient													
	Pre-Surgery		Surgery	Post-Surgery		2-weeks		6-weeks		3-months		6-months		9-months		12-months	
	Screening	Enrollment		≤ 48 hrs	Post Op												

Radiographs	•	•	•	•	•	•	•
Informed Consent	•						
Serum Creatinine*	•	•	•				
Randomization		•					
Intervention		•					
Baseline Data**			•				
Contact Information		•					
EQ-5D		•			•	•	•
Outcomes					•	•	•
Assessment***			•	•	•	•	•
FIX-IT					•	•	•
WPAI					•	•	•
C-reactive protein			•	•	•	•	•
Adverse Event					•	•	•
Screen			•	•	•	•	•

*** 2-week creatinine level will only be drawn if postoperative creatinine level is ≥ 1.5 times patient baseline and acute kidney injury is suspected

** demographic, medical history, injury characteristics

*** fracture-related infection, unplanned fracture-related reoperation

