5.2 Statistical Methods

Feasibility outcomes described in 4.7.1 will be summarized using means and proportions, without the use of inferential statistics. Given the principle feasibility aim of this pilot trial, the following statistical methods are described primarily for planning purposes. Statistical methodology to be performed in the analysis of each primary, secondary, and subsidiary outcome is outlined below. The statistical analysis plan (SAP) will provide additional detail on statistical analysis and will be modified as necessary based on data collected in this pilot trial.

Outcomes Analysis Planned for Definitive Trial

Outcome	Data	Method of analysis
---------	------	--------------------

Primary		
Rate of fracture-related infection	FRI criteria	Relative Hazard as estimated by two-sided binomial regression with the complementary log-log link, with a type I error rate (alpha) of 0.05.
Secondary		
Rate of unplanned reoperation	Review of complications	Fisher's exact test on the 2×2 cross-tabulation
Rate of nonunion	Nonunion criteria	
Subsidiary		
Quality of Life	EQ-5D	
Inflammatory Markers	CRP	
Radiographic Healing	mRUST	
Clinical Healing	FIX-IT	
Direct costs	TM Analysis	
Indirect costs	WPAI	
FRI Suggestive Criteria	FRI criteria	Fisher's exact test on the 2×2 cross-tabulation

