7.5 Adverse Event Reporting and Definitions

7.5.1 Adverse Event (AE)

An adverse event (AE) is the development of an undesirable medical condition or the deterioration of a pre-existing medical condition (not relevant in this study). AE's will be collected by means of a standard question on the follow-up questionnaire: "Have you developed any new health problems since the previous visit?" AE's will be recorded at every visit.

Spontaneously reported AE's and/or observed AE's will be recorded on a separate Adverse Events form with information about (1) date of onset and date of recovery, (2) seriousness, (3) severity and (4) outcome.

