7.5.3 Safety Monitoring

The following factors should be considered when deciding if there is a “reasonable possibility” that an Adverse Event may have been caused by the investigational product.

- Time course of events and exposure to drug – did the AE occur in a reasonable temporal relationship to the administration of the intervention?
- No alternative cause - the AE cannot be reasonably explained by another etiology such as an underlying disease (not previously present), other drugs, or environmental factors.

There would not be a “reasonable possibility” of causality if none of the above criteria apply or where there is evidence of exposure and a reasonable time course, but there is another more likely cause of the AE.

The subjects will additionally be asked to assess the **severity** of each reported Adverse Event according to the following scale:

Mild	= awareness of sign or symptom, but easily tolerated
Moderate	= discomfort sufficient to cause interference with normal activities
Severe	= incapacitating, with inability to perform normal activities.

Subjects will again be asked about the seriousness and severity of previously reported adverse events at subsequent follow-up visits, in order to track **outcome**.

Adverse Events believed to be secondary to intervention or standard of care with “reasonable probability” will be reviewed at interim analyses, and reported by the DSMC at that time to all required parties.

The Data and Safety Monitoring Committee (DSMC) for the study will consist of orthopedic surgeon [name] (Minneapolis, MN, USA), emergency medicine physician [name] (Dar es Salaam, Tanzania), and health services researcher [name] (Baltimore, MD, USA). [name] [name] will serve as the committee chair.

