7.5.4 Stopping Guidelines

The trial may be terminated for reasons of harm at the judgment of the DSMC. Several endpoints will be examined, including serious adverse events as described in the protocol. While the analysis would consider mal-distribution of predictive factors such as age, it is recognized that ethical considerations require careful considerations of statistical tests as well as qualitative

judgments in the light of experience. Any additional analyses required by the DSMC will be reported as needed.

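### Creatinine is drawn from everyone before surgery and on day 2, but no by-arm summary is planned, and a rise to 1.5 times baseline need not be rechecked unless kidney injury is also suspected

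*Combined protocol and SAP*

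**What the plan says.** **Measurement.** Section 4.4 (Schedule of Events) states that "serum creatinine will be obtained pre-operatively and on postoperative day 2". Section 4.3.1 (Patient Retention) adds that "Preoperative, postoperative, and 2-week creatinine levels will be covered for all participants".

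**Recheck.** The opening text of 4.4 says that if the day-2 value is at least 1.5 times baseline and "acute kidney injury is suspected, serum creatinine levels will be redrawn at two-week follow-up visit". The two-week visit item in 4.4 repeats both conditions. The Table 2 footnote opens "2-week creatinine level will only be drawn if postoperative creatinine level is" at least 1.5 times baseline, and then adds the same suspicion condition.

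**Analysis.** Creatinine is absent from the feasibility outcomes (2.2 and 4.7.1), from the primary, secondary, subsidiary and subgroup lists (4.7.2), and from the table and text of 5.2. C-reactive protein, the other scheduled blood test, is a listed subsidiary outcome and appears in the 5.2 table. Section 5.2 says the SAP "will provide additional detail on statistical analysis and will be modified as necessary based on data collected in this pilot trial".

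**Safety reporting.** Section 7.5.1 collects adverse events by a standard question, "Have you developed any new health problems since the previous visit", and also has spontaneously reported or observed events entered on a form. Section 7.5.3 sends to interim review "Adverse Events believed to be secondary to intervention or standard of care" with reasonable probability. Section 7.5.4 says "Several endpoints will be examined, including serious adverse events as described in the protocol". None of these mentions creatinine or a laboratory threshold.

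**The concern.** Participants in the gentamicin arm receive a local aminoglycoside, and the protocol itself treats kidney function as worth watching: it tests everyone and names a threshold. The day-2 values will exist in both arms, yet the plan as written produces no renal comparison from them.

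The redraw rule leaves a second gap. A rise that crosses the protocol's own threshold is followed up only if someone also suspects acute kidney injury, and no criteria for suspicion are given. For a participant without symptoms, the study might never learn whether the value returned to baseline.

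At stake are a small amount of safety information and the follow-up of a few participants. A later SAP could still add the table, but it could not recover a redraw that was not taken.

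**Working it through.** The plan states no renal figure to reproduce. The check is mainly a reading of the sections against each other, with arithmetic for scale.

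**1. Where creatinine is used**

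| Place | Creatinine or kidney injury mentioned? |
|---|---|
| 4.3.1 cost coverage | Yes |
| 4.4 text, two-week visit item, Table 2 and footnote | Yes |
| 2.2, 4.7.1 feasibility outcomes | No |
| 4.7.2 definitive-trial outcomes and subgroups | No |
| 5.2 table, 5.2.1, 5.2.2 | No |
| 7.5.1 to 7.5.4 adverse events, monitoring, stopping | No |

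**2. What the redraw rule does**

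| Day-2 value at least 1.5 times baseline | Kidney injury suspected | Study redraw at 2 weeks |
|---|---|---|
| Yes | Yes | Yes |
| Yes | No | Not required |
| No | Either | No |

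The middle row is the gap. All three statements of the rule give the same result.

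**3. How many participants fall in the middle row**

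Let p be the proportion of the 100 participants who reach the threshold and s the share of those in whom kidney injury is suspected. The documents give neither, so every value below is an assumption.

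Expected number not rechecked = 100 × p × (1 − s). Chance of at least one = 1 − (1 − p(1 − s))^100.

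| p | s | Expected | Chance of at least one |
|---|---|---|---|
| any | 100% | 0 | 0 |
| 2% | 95% | 100 × 0.02 × 0.05 = 0.1 | about 10% |
| 2% | 75% | 100 × 0.02 × 0.25 = 0.5 | 39% |
| 5% | 50% | 100 × 0.05 × 0.50 = 2.5 | 92% |
| 10% | 25% | 100 × 0.10 × 0.75 = 7.5 | over 99% |

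The result runs from zero to near certainty, depending on s. The documents do not narrow it.

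**4. What a by-arm summary could show**

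The Study Summary gives 50 per arm. For zero events among n, the exact two-sided 95% upper limit is 1 − 0.025^(1/n):

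- 0/50: 7.1%
- 0/45: 7.9%
- 0/40: 8.8%

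The last two apply if some participants lack one of the two values. For non-zero counts, Clopper-Pearson gives 0.5% to 13.7% for 2/50 and 3.3% to 21.8% for 5/50. Intervals this wide support description only.

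**5. Exposure and cost**

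The solution is 2 mg/mL and the volume 5 to 40 mL, so the gentamicin-arm dose is 2 × 5 = 10 mg to 2 × 40 = 80 mg. Threshold rises per arm at the assumed 2% to 10%: 50 × 0.02 = 1 to 50 × 0.10 = 5. This is the most that extra redraws or forms could number, since some would have occurred anyway.

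**The case against.** - **The redraw rule may be looser than it looks.** The sentence cites an acute kidney injury guideline, so reaching the threshold may itself be meant to raise suspicion. Treating clinicians can also repeat the test as ordinary care. This stands as a reason not to predict how many rises would be missed. It does not remove the second condition from the text, and if the two conditions were meant as one, deleting the second costs nothing.
- **Adverse-event logging already has a route.** Section 7.5.1 requires observed events to be recorded, and a protocol-ordered result crossing a protocol threshold is a natural candidate. Table 2 has an adverse event screen row, although its columns cannot be read reliably here. Section 3.1 points to accompanying operating procedures and 6.1 to case report forms, which were not available and may hold the instruction. This largely stands, so the logging part is a request for clarification.
- **The DSMC is not confined to serious events.** The list in 7.5.4 is open, and the committee may ask for more analyses. This stands.
- **This is a feasibility pilot.** It is, and nothing here touches its endpoints. The values are being collected anyway, and the pilot is meant to inform the definitive trial.
- **Coded-arm counts could threaten masking.** There are only two fixed syringe labels, so a visible renal imbalance between Solution A and Solution B could suggest the whole allocation key. This stands and shapes the fix.

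**Conclusion.** The point holds as a cheap improvement of minor importance. Creatinine from all participants has no planned by-arm summary, and the redraw rule as worded allows a threshold rise to go unchecked by the study when kidney injury is not suspected. Both statements rest on the current text alone; the frequency of the second cannot be estimated from it.

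A reader might infer four stronger things that the documents do not support:

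- **That missed rechecks are likely.** The high probabilities in the table depend on assumed suspicion shares of 25% to 75%; at shares close to 100% they fall towards zero.
- **That renal harm is expected.** The dose range of 10 to 80 mg describes exposure, not toxicity, and no event rate is given.
- **That kidney injury would go unrecorded or be hidden from the DSMC.** The observed-event route and the committee's open remit both exist.
- **That 4.3.1 contradicts 4.4.** Paying for a 2-week test for any participant is compatible with drawing it conditionally.

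**What to change.** 1. **Redraw.** Remove the suspicion condition from the two redraw sentences in 4.4 and from the Table 2 footnote, so that every day-2 value of at least 1.5 times baseline is rechecked at the 2-week visit. That visit already takes blood for C-reactive protein, and 4.3.1 already covers the test. A 2-week draw for everyone is not needed.
2. **Summary.** Add a descriptive safety item to 4.7 (Outcome Measures) and 5.2: number and proportion per arm with day-2 creatinine at least 1.5 times baseline, exact 95% confidence interval, and median change from baseline, among participants with both values. No hypothesis test.
3. **Clarification.** State in 7.5.1 that a threshold rise counts as an observed adverse event. During the trial, have counts by coded arm prepared by unmasked personnel and sent only to the DSMC. The Masking section says these personnel do not know any participant's group, so this access should be written in as a stated exception.

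**Cost.** Protocol wording, one table, and at most about 1 to 5 extra redraws and forms per arm if 2% to 10% meet the threshold (assumed). The masking risk is contained by the restricted circulation. Feasibility endpoints, primary analysis and sample size stay as they are.

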4.5 Randomization Methods

Allocation to the study groups will be randomly assigned using a web-based randomization tool as part of Research Electronic Data Capture (REDCap). The randomization sequence was generated using randomly permuted blocks of 4, 6, and 8 with a 1:1 allocation ratio.

4.6 Masking:

Trial participants are masked to treatment group allocation. All health care providers involved in care of the trial participants including physicians, surgeons, and nurses are masked to treatment group allocation. Research team members including research coordinators, data collectors, and data analysts, are masked to treatment group allocation.

Masking is established and maintained by preparation of the study solutions in visually indistinguishable syringes labeled either “Solution A” or “Solution B”.

Two UCSF research personnel are unmasked for the implementation and management of trial protocols, but do not have any contact with study participants and are not aware of the treatment group to which each participant is assigned. The study nurse responsible for preparation of study solutions at MOI is also unmasked, but does not have any contact with study participants and is not aware of the treatment group to which each participant is assigned.

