4.6 Description of Data Collection

4.6.1 Data collection

Three trained research coordinators with research and data collection experience will be responsible for all data collection. All data will be uploaded into REDCap (see section **6.0 DATA MANAGEMENT**) using portable laptops and tablet computers.

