4.7 Outcome Measures

4.7.1 Feasibility Trial Outcomes

7. Recruitment: number of patients screened, number and proportion of patients screened that are eligible, enrolled, randomized, and receive intervention.
8. Retention: number and proportion of randomized patients who attend each follow-up visit. We aim for an adherence rate at follow-up of 80% at one year, which was achieved in our previous open tibia fracture trial performed through the same collaborative partnership.
9. Data collection completeness: proportion of fracture-related infection criteria, EuroQol-5 Dimensions, 3-level questionnaire (EQ-5D), Function Index for Trauma (FIX-IT), and

Modified Radiographic Union Score for Tibia (mRUST)¹⁷ indices complete at each time-point.

10. Solution quality control: confirmation of the ongoing sensitivity of standard organisms to trial solutions via interval testing. This will occur once per month for the first 6 months and once every 6 months thereafter by the Muhimbili University of Health and Allied Sciences (MUHAS) microbiology lab, with results evaluated by unmasked study personnel.
11. Masking and concealment: determination of the continued masking of surgeons to solution identity via intraoperative surgeon survey.
12. Evaluation of primary and secondary outcomes: reliability of fracture-related infection and mRUST scoring, validation of telephone criteria for fracture-related infection, radiographic image quality, and completeness of EQ-5D and FIX-IT.

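### Telephone FRI criteria are to be validated, but nothing keeps the answers from whoever records FRI at the visit, and the plan defines neither the reference standard nor how repeat pairs are counted

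*Combined protocol and SAP*

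**What the plan says.** Item 12 of 4.7.1 Feasibility Trial Outcomes includes "validation of telephone criteria for fracture-related infection". The parallel list in section 2.2 does not mention it.

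Section 4.4 describes how the data arise. At 6 weeks, and in the same words for 3, 6, 9 and 12 months: "During the follow-up visit reminder telephone phone call, the study investigator will ask the five fracture-related infection (FRI) validation questions". Of the clinic contact it says: "At the visit, the study investigator will review and record interval history since the last appointment". The examination sentence is in the passive and names nobody: "A physical examination will be performed to assess for signs of fracture-related infection (FRI". No validation call is described for the 2-week visit.

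On timing, section 4.3.1 says: "Follow-up clinic visit reminders will be given via phone call and by text message during the week prior to each visit". On staff, section 4.6.1 says: "Three trained research coordinators with research and data collection experience will be responsible for all data collection". Everything goes into one REDCap system. On masking, section 4.6 Masking says: "Research team members including research coordinators, data collectors, and data analysts, are masked to treatment group allocation". It says nothing about masking anyone to the telephone answers.

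Section 5.2 summarises feasibility outcomes by means and proportions, without inferential statistics, and leaves further detail to the SAP. No text names a comparator, an accuracy measure or a unit of analysis for the telephone validation.

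**The concern.** A validation study compares an index test with a reference judgement made without knowledge of it. Here the index test is the set of five telephone questions. The natural reference is the FRI assessment at the visit about a week later. If the assessor knows the answers, they can steer what is asked, looked for and recorded, and agreement rises for reasons unrelated to the quality of the questions.

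A second problem does not depend on who examines. Each patient can supply up to five call-visit pairs. Once an FRI is known, later calls and visits may agree because both sides know the diagnosis. If those pairs are pooled with the pair at which the infection was found, they count as successful detection.

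At stake is one stated feasibility outcome. A telephone tool would be most useful for patients who do not attend, and section 5.1 plans for 20% loss. That use is an inference, because the protocol does not say the definitive trial will rely on telephone FRI status.

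**Working it through.** **1. The plan's own figures.** The documents give no number for the telephone validation. The infection rates come from section 5.1: 12% in controls, halved to 6%. They reproduce the stated sample size with the pooled-variance formula, two-sided alpha 0.05 and power 0.80:

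n = [1.960·√(2·0.09·0.91) + 0.842·√(0.12·0.88 + 0.06·0.94)]² / 0.06² = 356 per group, 712 in total; 712/0.80 = 890.

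This confirms the inputs. The point itself does not touch these figures.

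**2. Who does what, from the text.**

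| Step | Assigned to | Kept unaware of telephone answers? |
|---|---|---|
| Telephone questions (4.4) | the study investigator | not applicable |
| Interval history at visit (4.4) | the study investigator | not required |
| FRI examination at visit (4.4) | not named | not required |
| Adjudication (Study Summary; 4.7.3) | Steering Committee | not stated |

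The Study Summary promises blinded adjudication of FRI, but 4.7.3 lists only deaths and complications requiring reoperation for review. Neither place ties adjudication to the telephone validation.

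**3. How much information there is.** Expected FRIs: 0.12·50 + 0.06·50 = 6 + 3 = 9. After 20% loss: 9·0.80 = 7.2. The maximum number of pairs is 5·100 = 500. Exact (Clopper-Pearson) 95% intervals for sensitivity:

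- 7 of 9: 0.40 to 0.97
- 5 of 7: 0.29 to 0.96

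Any FRI diagnosed at 2 weeks, before the first call, reduces these counts further.

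**4. Direction of the bias (illustration, assumed inputs).** Assume true telephone sensitivity 0.70, specificity 0.90 and prevalence p = 0.09 (the mean of 12% and 6%, per patient). Let k be the probability that the recorded visit result simply follows the telephone result. With a perfect examination:

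apparent sensitivity = [p·0.70 + (1−p)·0.10·k] / [p·0.70 + (1−p)·0.10·k + p·0.30·(1−k)]

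At k = 0.25: (0.0630 + 0.02275) / (0.0630 + 0.02275 + 0.02025) = 0.08575/0.1060 = 0.81.

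The same model was run with an imperfect examination (sensitivity 0.90, specificity 0.98). Apparent sensitivity/specificity:

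| k | Perfect examination | Imperfect examination |
|---|---|---|
| 0 | 0.70 / 0.90 | 0.59 / 0.89 |
| 0.10 | 0.75 / 0.91 | 0.65 / 0.90 |
| 0.25 | 0.81 / 0.92 | 0.73 / 0.92 |
| 0.50 | 0.89 / 0.95 | 0.84 / 0.95 |

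Within each column, knowledge of the answers pushes accuracy up. Against the assumed truth of 0.70, the imperfect-examination result is still too low at k = 0.10 and is too high from k = 0.25.

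**5. Repeat pairs (illustration, assumed inputs).** With sensitivity 0.70 at the diagnosing pair, r later pairs per FRI and a proportion g of those positive on both sides (the rest being visit-positive and telephone-negative), pooled sensitivity is (0.70 + r·g)/(1 + r):

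- r = 1, g = 1: 1.70/2 = 0.85
- r = 2, g = 1: 2.70/3 = 0.90
- r = 2, g = 0.70: 2.10/3 = 0.70
- r = 2, g = 0.50: 1.70/3 = 0.57

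The result depends wholly on r and g. The documents give neither, nor the wording of the five questions.

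**The case against.** A reader might infer that the plan has one person hear the answers and then at once carry out the FRI assessment, so that accuracy is bound to be inflated. The documents do not support that.

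- The shared label covers the call and the interval history only; the examiner is unnamed. It is a role, and with three coordinators the caller and the history-taker may be different people.
- The call falls in the week before the visit, not immediately before it.
- That the visit is the reference standard is a reasonable inference, not written text.
- FRI rests on four confirmatory criteria (4.7.2 Definitive Trial Outcomes). Interval history is not one of them, and culture and histopathology are hard to sway by a remembered telephone answer.
- No section prescribes pooling of repeat pairs.
- With an imperfect examination and little influence from the answers, apparent sensitivity can lie below the truth.
- A bias of several points is small beside an interval of 0.40 to 0.97, and telephone validation is one clause of one feasibility item.

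All of this stands, and it limits the claim to what may happen. It does not remove the gap. Even if different people call and assess, nothing keeps the answers from the assessor. Clinical signs such as wound breakdown or drainage remain open to influence. The imprecision is a reason to report intervals; it does not excuse an avoidable bias.

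**Conclusion.** The concern holds in limited form. A stated feasibility outcome has no named reference standard, no named assessor, no masking of that assessor to the telephone answers and no rule for repeated pairs. Apparent telephone accuracy may be overstated. The size is unknown: the figures in steps 4 and 5 of the working rest on assumed accuracies and should not be quoted as estimates for this trial.

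What follows from the documents' own rates is that sensitivity will rest on about 9 infections, or about 7 after 20% loss, and will be imprecise whatever is done. This assumes that the 12% deep-infection rate carries over to FRI and that the hoped-for halving occurs. The definitive trial's sample size and alpha are not affected. The matter deserves attention before enrolment because masking cannot be restored once the visits have taken place.

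**What to change.** **Section 4.4.** Have a different one of the three existing coordinators make the call from the person who takes the visit history and records the FRI criteria. Lock the telephone form in REDCap and keep it from that assessor only until the visit FRI criteria are recorded. State that this does not change how reported symptoms reach the treating team.

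**Section 4.7.1 Feasibility Trial Outcomes, item 12.** Name the reference standard: FRI criteria recorded at the visit by the masked assessor. Report sensitivity and specificity of the call with exact confidence intervals, using each patient's pairs up to and including the one at which FRI is first confirmed. Sensitivity then has at most one pair per infected patient. Give specificity visit by visit, so that no patient counts more than once in an interval. Say how an FRI confirmed between visits is handled.

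**Section 5.2.** Allow these intervals explicitly, since feasibility outcomes are otherwise to be summarised without inferential statistics.

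**Cost.** Task allocation among existing staff, a REDCap access setting and a few sentences. The downsides are a rota constraint on clinic days and incomplete independence: the assessor may hear the same symptoms from the patient, so the change reduces the bias without removing it.
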